Prostate Volume ^e Measurement (via ultrasound)		X ^e											
Uroflowmetry	X											X	
Urodynamics ^f		X						X					
Laboratory Assessments ^g	X		X			X		X				X	
Dispense Bladder Diary ^h	X	X	X		X	X	X	X		X			
Dispense Run-in Study Drug		X											
Dispense Double-blind Study Drug ⁱ			X			X	X	X		X			
Administer Witnessed Dose of Study Drug		X	X										

AE = adverse event; BPH = benign prostatic hypertrophy; ECG = electrocardiogram;

IPSS =

International Prostate Symptom Score; IWRS = interactive web response system; OAB = overactive bladder;

PGI =

Patient Global Impression; PRO = patient-reported outcomes; PVR = Post-void residual; SAE = serious adverse event; WD = withdrawal

NOTE: Certain study assessments and procedures also may be performed remotely to minimize contact, as outlined in Section 8.6.

* To account for additional time that may be necessary to ensure safety through COVID-19 preventive measures, a COVID Mitigation Window, with extended windows for visit timings, has been implemented. However, if safe and feasible, study visits should adhere to the schedule outlined Visit Window when.

a With the exception of prostate volume measurement (which can be completed any time prior to randomization), all Screening procedures and the initial 3-day Bladder Diary must be completed prior to Run-In (Visit 2).

b The Safety Follow-up is not applicable for subjects who enter the extension study (URO-901-3006).

- d Vital signs (including blood pressure [triplicate], pulse, body temperature, respiration rate, and weight) should be taken prior to blood draws and study drug dosing; height is measured at Screening only.
- e A historical prostate volume measurement by ultrasound, performed within 12 months prior to the first day of Screening, is acceptable if the criteria detailed in [Section 8.3.8](#) are satisfied. For subjects with no acceptable historical measurement, a prostate volume measurement by ultrasound must be completed prior to randomization (Baseline/Visit 3).

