Secondary Efficacy 
 To assess the efficacy of vibegron compared with placebo in men with OAB symptoms on pharmacological therapy for BPH as defined by other key measures 	Secondary Efficacy 
 CFB at Week 12 in the average number of nocturia episodes per night CFB at Week 12 in the average number of urge urinary incontinence episodes per day for subjects with urinary incontinence at baseline CFB at Week 12 in the IPSS Storage score (1-week recall) CFB at Week 12 in the average volume voided per micturition
Safety 
 To assess the safety and tolerability of vibegron compared with placebo in men with OAB symptoms on pharmacological therapy for BPH 	Safety 
 AEs, concurrent medications, clinical laboratory, vital sign assessments, PVR volume, uroflow measures, IPSS, urodynamics (sub-study only)
Other Efficacy 	Other/Exploratory - Efficacy 
 CFB at Week 2, Week 4, Week 8, Week 16, Week 20 and Week 24 in the average number of micturition episodes per day CFB at Week 2, Week 4, Week 8, Week 16, Week 20, and Week 24 in the average number of urgency episodes per day CFB at Week 2, Week 4, Week 8, Week 16, Week 20 and Week 24 in the average number of nocturia episodes per night CFB at Week 4, Week 8, Week 20, and Week 24 in the IPSS Storage score (1-week recall) CFB at Week 4, Week 8, Week 12, Week 20, and Week 24 in the IPSS Quality of Life score (1-week recall) CFB at Week 4, Week 8, Week 12, Week 20, and Week 24 in the IPSS Voiding score (1-week recall) CFB at Week 2, Week 4, Week 8, Week 16, Week 20, and Week 24 in the average number of urge urinary incontinence episodes per day for subjects with urinary incontinence at baseline CFB at Week 2, Week 4, Week 8, Week 16, Week 20, and Week 24 in the average volume voided per micturition CFB at Week 2, Week 4, Week 8, Week 12, Week 16, Week 20, and Week 24 in the average number of total incontinence episodes per day for subjects with urinary incontinence at baseline

- Percent of all subjects with a 50% reduction from baseline in average urgency episodes (urgency: need to urinate immediately) per day at Week 2, Week 4, Week 8, Week 12, Week 16, Week 20, and Week 24

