4.2.4.2. Analysis Visit Windows

Analysis visit windows for both diary and non-diary data are defined as shown in Table 3. All observations will be given an analysis visit, assigned based on relative study day, as defined in section 4.3.3. If fewer than three diary days are within the analysis window, only the data within the window will be used to calculate visit-level averages. Unless otherwise noted, all data will be listed.

Table 3: Analysis Window Slotting

Analysis window label	Nominal visit	Nominal day	Non-Diary Visit Window	Diary Visit Window
Screening	Visit 1	-49 to - 21	date of informed consent to date of first run-in dose	
Run-in	Visit 2	-14	date of first run-in dose to day -1	7 days prior to date of first run-in dose
Baseline	Visit 3	1	[-1,1]	date of first run-in dose to day -1
Week 1	Visit 4	8	[2, 11]	
Week 2	Visit 5	15	[12, 22]	[7, 18]
Week 4	Visit 6	29	[23, 42]	[19, 39]
Week 8	Visit 7	57	[43, 70]	[47, 67]
Week 12	Visit 8	85	[71, 98]*	[68, 102]
Week 16	Visit 9	113	[99, 126]	[103, 123]
Week 20	Visit 10	141	[127, 154]	[131, 151]

Analysis window label	Nominal visit	Nominal day	Non-Diary Visit Window	Diary Visit Window
Week 24	Visit 11	169	[155, last dose date + 5]	[159, 179]
Follow-Up for Early Withdrawals	NA	NA	>Last dose date + 5	
Follow-Up for Completers	NA	NA	>Last dose date + 5	

*Urodynamics window for Week 12 is [57, 113]

For subjects who withdraw early, assessments taken at the end of study visit will also be summarized with scheduled data if they fall within an on-study visit window and are within 21 days after the last treatment date.

For parameters which were **not** scheduled to be collected at all visits, still use the all-inclusive visit intervals defined for all visits (i.e., the window defined above) to slot records. However, if a value is slotted to a visit unscheduled for a parameter, it will not be summarized (and not be included in the efficacy datasets) but will be included in data listings.

1. If after all records have been slotted, there are multiple valid records within a visit, use the record by the following the rules below:
 - If there are more than three bladder diary days within the window, the three days closest to the nominal visit day will be used to calculate analysis visit averages. If two days are equidistant to the nominal visit day, the earlier day will be selected first.

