 - If there are multiple values for other efficacy endpoints in one window, the visit closest to the nominal day will be selected for assessing endpoints at a particular visit and for by-visit displays. If the visits are equidistant from the nominal day, then the earlier visit will be selected. All values will be stored in analysis datasets.
 - The same visit windows will be used for safety and laboratory assessments. If there are multiple safety or laboratory values in one time window on-treatment, the worst value (furthest from the center of the normal range if both high and low abnormalities exist) will be selected for the by-visit analyses.

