9.3. COVID-19 Considerations

The COVID-19 global pandemic developed during the conduct of the study. The recommended impact analysis was therefore added to the SAP, as the operational change of increased visit windows had been initially communicated via study memo with no protocol amendment. COVID-19 expanded visit windows are spelled out in Protocol Amendment 2; 6-week visit extensions due to COVID-19 were available starting in March 2020.

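### SAP Table 3 closes the non-diary Week 12 window at Day 98, so a protocol-permitted late Visit 8 IPSS in Part 2 (Days 99 to 126) is not analysed as Week 12 and is left out of the efficacy datasets

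*SAP*

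**What the plan says.** **Protocol.** The Part 2 Schedule of Assessments (Section 1.4) places Visit 7 at Day 57 and Visit 8 at Day 85, each ± 4 days. A footnote adds that "a COVID Mitigation Window, with extended windows for visit timings, has been implemented"; it gives +3 weeks for Visit 7 and +6 weeks for Visit 8. The footnote asks sites to keep to the normal window where safe and feasible. SAP 9.3 confirms that "6-week visit extensions due to COVID-19 were available starting in March 2020".

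Part 2 schedules the IPSS at Visits 7, 8 and 10 but not at Visit 9 (Week 16), which is a remote call with no IPSS in its procedure list (Section 10.7.9). Apart from Week 12, the listed IPSS Storage endpoints (Section 3) are "CFB at Week 4, Week 8, Week 20, and Week 24 in the IPSS Storage score (1-week recall"). Section 8.2 has questionnaires completed at the visit or just before it, so the IPSS date moves with the visit date.

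**SAP 4.2.4.2.** "All observations will be given an analysis visit, assigned based on relative study day". The non-diary windows are Week 8 [43, 70], Week 12 [71, 98], Week 16 [99, 126] and Week 20 [127, 154]. Only urodynamics has a wider Week 12 window, Days 57 to 113. When several efficacy values fall in one window, "the visit closest to the nominal day will be selected for assessing endpoints at a particular visit", and ties go to the earlier visit. For a parameter not collected at every visit, "if a value is slotted to a visit unscheduled for a parameter, it will not be summarized", and it is also kept out of the efficacy datasets; such a value appears in listings only.

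**The concern.** The protocol treats a Visit 8 held on, say, Day 110 as a permitted Week 12 visit. The SAP treats its IPSS as a Week 16 value and, for a Part 2 subject, sets it aside. The repeated-measures model then handles as missing at random a score that was in fact collected.

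The opposite error can occur too: a Visit 7 score taken late, but within its permitted window, can enter the model as Week 12.

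The endpoint exposed is the change in IPSS Storage score at Week 12, third in the testing sequence of SAP 4.1.2. A failure there also stops formal testing of volume voided per micturition, which is fourth.

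**Working it through.** **1. The SAP window reproduces.** Table 3 uses midpoints between nominal days: (57 + 85)/2 = 71 and (85 + 113)/2 = 99, hence Week 12 = [71, 98]. The window is internally regular; it simply takes no account of the extension.

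**2. Protocol limits.**
- Visit 8: earliest 85 − 4 = Day 81; latest 85 + 6 × 7 = Day 127.
- Visit 7: earliest 57 − 4 = Day 53; latest 57 + 3 × 7 = Day 78.
- This counts the extension from the nominal day. If it were added to the +4 days, the Visit 8 limit would be Day 131.

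**3. A Part 2 Visit 8 IPSS passed through Table 3.**

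| Visit 8 held on | Days | Table 3 label | IPSS scheduled there in Part 2? | Result |
|---|---|---|---|---|
| Days 81–98 | 18 | Week 12 | Yes | Kept as Week 12 |
| Days 99–126 | 28 | Week 16 | No | Listed only |
| Day 127 | 1 | Week 20 | Yes | Relabelled Week 20 |

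The total is 18 + 28 + 1 = 47 permitted days. Under the Day 131 reading, Days 127 to 131 (5 days) go to Week 20. These are calendar days, not subjects.

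**4. A late Visit 7 IPSS.** Days 71 to 78 (8 of the 26 permitted days) fall in the Week 12 window, at distances of 85 − 78 = 7 to 85 − 71 = 14 days from nominal.
- If Visit 8 falls after Day 98, the Visit 7 score is the only one in the window and becomes Week 12.
- If Visit 8 falls on Days 92 to 98 (distances 7 to 13), the Visit 7 score is used whenever it is at least as close. Example: Visit 7 on Day 78 and Visit 8 on Day 92 tie at 7 days, and the earlier is taken.
- If Visit 8 is on time (at most 4 days from Day 85), it always wins.

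**5. Effect on precision.** The documents do not say how many Visit 8 dates fell after Day 98. Take an assumed lost fraction f of the 924 planned evaluable subjects; without borrowing from other visits, the standard error is multiplied by 1/√(1 − f).

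| f (assumed) | Scores lost, 924 × f | SE multiplier |
|---|---|---|
| 1% | 9 | 1.005 |
| 5% | 46 | 1.026 |
| 10% | 92 | 1.054 |

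These are upper figures for each f, because the model also uses the other visits' IPSS scores.

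**The case against.** Midpoint windows are a standard and defensible choice. SAP 9.3 shows that the authors knew of the 6-week extension, and a score taken 6 weeks late is not obviously a Week 12 outcome. A bottle holds 32 tablets, a 4-week supply (Protocol 6.1), so a delayed visit may follow a gap in drug supply. SAP 3.2 removes from the per-protocol set anyone whose visit delay caused more than 14 days without study drug, and the primary model is described as using on-treatment values. All of this stands, and it is why the present windows should survive as a sensitivity analysis. It does not explain why urodynamics received a wider Week 12 window and the IPSS did not.

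It can also be argued that the late score is not dropped at all. Part 1 schedules the IPSS at Visits 9 and 10, the two parts are pooled, and SAP 6.3.1 admits Week 16 data where collected. For Part 1 that is right: a score slotted to Week 16 would be relabelled and kept. For Part 2, planned at about 1008 of 1088 subjects, the schedule has no Week 16 IPSS, and the exclusion rule read against that schedule removes the score. On either reading it is lost from Week 12.

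Four stronger readings are tempting and are not supported:
- **That most Week 12 scores are at risk**, because only 18 of 47 permitted days keep the label. The normal window, Days 81 to 89, lies wholly inside [71, 98], and the extension is an exception.
- **That the co-primary endpoints are compromised.** Protocol Table 1 ties the Week 12 diary to Days 78 to 84, and the SAP diary window is [68, 102].
- **That vital signs and residual volume are lost in the same way.** Part 1 schedules both at Week 16, and SAP 7.3.1 and 7.5 describe them as collected or summarised at essentially every visit. By-visit labels may shift, but SAP 4.2.2 keeps assessments from unscheduled visits in the maximum, minimum and any-time summaries.
- **That the treatment comparison is biased.** Nothing in the documents shows that delays differ by arm in this double-blind trial.

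**Conclusion.** The protocol's permitted Week 12 window and SAP Table 3 disagree for the IPSS. In Part 2, a Visit 8 score on Days 99 to 126 loses its Week 12 label and is left out of the efficacy datasets; one on Day 127 moves to Week 20. A permitted Visit 7 score on Days 71 to 78 can take the Week 12 place, but only if Visit 8 falls after Day 98, or on Days 92 to 98 and no nearer to Day 85.

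The consequence is avoidable loss and mislabelling of collected data for one sequence-tested secondary endpoint. On the assumed range of 1% to 10% lost, the cost in precision is at most about 0.5% to 5% in standard error. Any bias cannot be computed from the documents. The conclusion rests on counting the extension from Day 85 and on reading the exclusion rule against the Part 2 schedule. The point is worth correcting because the remedy is cheap, not because the likely effect is large.

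**What to change.** Before unblinding, add a footnote to SAP Table 3 stating that:

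1. an IPSS collected at nominal Visit 8 within the protocol-permitted window (to Day 127) is analysed as Week 12;
2. an IPSS collected at nominal Visit 7 is never used as the Week 12 value when a Visit 8 IPSS exists;
3. true Visit 9 scores in Part 1 remain Week 16.

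The rule should follow the nominal visit. Merely stretching the window to Day 126 would miss Day 127 and could turn a Part 1 Week 16 score into a Week 12 one. Keep the [71, 98] study-day slotting as a sensitivity analysis for IPSS Storage, and report how many Visit 8 scores fell after Day 98 in each arm.

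The cost is one footnote and one additional model run. The drawback is that some Week 12 scores will be up to 6 weeks late and may follow an interruption in drug supply. The sensitivity analysis and the per-protocol rule on more than 14 days without study drug address this.

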4.3. Data Definitions and Derivations of Endpoints

4.3.1. Bladder Diary Endpoints

The bladder diary recorded what time subjects woke up for the day, what time they went to bed, and asked the subjects to record every time they had a urination event or leakage. For each event, subjects recorded the time, if they had a need to urinate immediately, if they urinated in the toilet, if they had accidental urine leakage and if they had leakage the main reason for the leakage (urge or other) for 3 consecutive days, and volume voided per micturition (over one 24-hour period) prior to each required timepoint. The following efficacy parameters will be derived based on the Diary data for baseline, Weeks 2, 4, 8, 12, 16, 20 and 24. Parameters will be derived

for the visit only if there is at least one valid diary day within the analysis window. If a subject answered ‘no’ to all three questions for every record on a diary day, with no volume recorded on any record, that day will be treated as missing for analysis purposes but will be included in the listings.

4.3.1.1. Co-primary Efficacy Endpoint

Although these endpoints are automatically derived in eCRF Day 3 Bladder Diary page, the final statistical analysis will use the value derived by the biometrics team based on the algorithm described below.

CFB in average number of daily micturition episodes to Week 12 (co-primary endpoint)

The number of micturition episodes will be defined as the number of times a subject has voided in the toilet as indicated on the Bladder Diary, either by marking the ‘urinated in toilet’ question as yes or recording a non-zero volume voided. This will be derived from individual log lines within each diary day; automatically derived daily totals on the eCRF Bladder Diary pages will not be used. Average number of micturition episodes per day at each study visit will be calculated using records within the diary analysis visit windows described in Table 3 divided by non-missing diary days (diary days with at least one void reported).

CFB in average number of daily urgency episodes to Week 12 (co-primary endpoint)

The number of urgency episodes will be defined as the number of times a patient has checked that he had the need to urinate immediately as indicated on the Bladder Diary. Average number of daily urgency episodes at each study visit will be calculated as the total number of urgency episodes within the diary analysis visit windows divided by non-missing diary days.

4.3.1.2. Secondary Efficacy Endpoint (Bladder Diary)

CFB in average number of daily nocturia episodes to Week 12 (secondary endpoint #1)

Nocturia episodes will be calculated in the same manner as average number of daily micturition episodes but only include episodes occurring during sleep (after bedtime on the current diary day and prior to wake-up time on the subsequent day). Although the endpoint is automatically derived in eCRF Day 3 Bladder Diary page (and daily totals are automatically derived on the eCRF Bladder Diary pages), the final statistical analysis will use the value derived by the biometrics team based on the algorithm described above.

CFB in average number of daily urge urinary incontinence (UUI) episodes to Week 12 for subjects with UI at baseline (secondary endpoint #2)

The number of UUI episodes will be defined as the number of times a subject has checked that they had “urge” as the main reason for the leakage. Average UUI episodes per day at each study visit will be calculated in the same manner as described above for the micturition endpoint. The UUI endpoint will be analyzed for subjects with UI at baseline.

CFB in average volume voided per micturition to Week 12 (secondary endpoint #4)

The total volume voided will be calculated using all urinary volumes collected regardless of whether patients checked “Urinated in Toilet or not”. Average volume voided per micturition at each study visit will be calculated as the total volume voided over diary days within the analysis visit window divided by the total number of micturition episodes with recorded volume.

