9.3. Populations for Analyses

Analysis Populations

Screened Set

The Screened Set consists of all subjects who are screened for the study. This population is used primarily for subject accounting purposes and will generally not be used for summary or analysis.

Run-in Set

The Run-in set consists of all subjects who entered the run-in period of the study. Subjects will be considered run-in failures if they enter the run-in period but are not randomized to receive double-blind medication.

Randomized Set

The Randomized Set consists of all subjects who are randomized to receive study medication regardless of whether they take a dose.

Safety Analysis Set (SAF)

The Safety Analysis Set consists of all subjects who receive at least one dose of double-blind study medication. Subjects will be classified according to the treatment they actually received.

Full Analysis Set (FAS)

The Full Analysis Set (FAS) population will serve as the primary population for the analysis of efficacy data in this trial. Since the endpoints related to incontinence only apply to subjects who meet the definition of incontinence at trial entry, it is necessary to have a separate FAS definition with an additional criterion to define the primary analysis population for incontinence endpoints.

FAS consists of all randomized subjects who took at least one dose of double-blind study medication and have at least one evaluable change from baseline micturition measurement. Subjects will be analyzed according to their randomized treatment, irrespective of premature discontinuation, according to the Intent-to-Treat (ITT) principle.

Full Analysis Set for Incontinence(FAS-I)

FAS-I consists of all randomized subjects with incontinence at baseline who took at least one dose of double-blind study medication, have an evaluable baseline urgency urinary incontinence measurement, and have at least one evaluable change from baseline urgency urinary incontinence measurement.

Note that “subjects with incontinence at baseline” are defined as meeting the following criteria:

- An average of ≥ 8.0 micturitions per Diary Day
- An average of ≥ 1.0 urinary incontinence episodes per Diary Day

Per-Protocol Set (PPS) and Per-Protocol Set for Incontinence (PPS-I)

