3.1.6. Full Analysis Set

The Full Analysis Set (FAS) population will serve as the primary population for the analysis of efficacy data in this trial. Since the endpoints related to incontinence only apply to subjects who meet the definition of incontinence at trial entry, it is necessary to have a separate FAS definition with an additional criterion to define the primary analysis population for incontinence endpoints.

The following FAS populations are defined in the study:

- **Full Analysis Set (FAS):** consists of all randomized subjects who took at least one dose of double-blind study medication and have at least one evaluable change from baseline micturition measurement. Subjects will be analyzed according to their randomized treatment, irrespective of premature discontinuation, according to the Intent-to-Treat principle.
- **Full Analysis Set for Incontinence (FAS-I):** consists of all randomized subjects with incontinence at baseline (as calculated from the baseline diary) who took at least one dose of double-blind study treatment and have at least one evaluable change from baseline urinary incontinence measurement.

Note that “subjects with urinary incontinence at baseline” are defined as meeting the following criteria based on the 3-day bladder diary completed by the subject during the Run-in period:

- An average of ≥ 8.0 micturitions per Diary Day. A “Diary Day” is defined as the time between when the subject gets up for the day each morning (i.e., the time the subject got up for the day yesterday to the time the subject got up for the day today; approximately a 24-hour period).
- An average of ≥ 1.0 urinary incontinence episodes per Diary Day

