4.3.1.3. Other Exploratory Efficacy Endpoints

Average number of daily urinary incontinence (UI) episodes for subjects with UI at baseline (exploratory)

Average number of urinary incontinence episodes per day will be calculated as the total number of “Accidental Urine Leakage” regardless of the choice of “Main Reason for Leakage” over diary days within the analysis visit window divided by non-missing diary days.

Urgency episodes 50% daily responder (exploratory)

The achievement of at least a 50% reduction from baseline in average daily urgency episodes is a binary variable of 0 (endpoint is not attained) or 1 (endpoint is attained). Subjects will be considered as responders when the endpoint is attained.

Urgency urinary incontinence (UII) episodes daily 75% responder (exploratory)

The achievement of at least a 75% reduction from baseline in average daily UII episodes is a binary variable of 0 (endpoint is not attained) or 1 (endpoint is attained). Subjects will be considered as responders when the endpoint is attained. The endpoint will be analyzed for subjects with UI at baseline.

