4.3.4. Baseline and Change from Baseline

In general, the last recorded value on or prior to the date of randomization will serve as the baseline measurement for efficacy endpoints while the last recorded value prior to first double-blind dose of study treatment will serve as the baseline measurement for safety endpoints. The mean of multiple values will be used as baseline for the following situations:

- If multiple measurements are scheduled on the same baseline day (i.e., blood pressure)
- If multiple measurements are collected on the same baseline day without the time or “repeat” status to differentiate the records

For efficacy endpoints derived from the Bladder Diary, the baseline will be the average value over the diary days in the baseline analysis visit window.

Change from baseline will be calculated as the post-baseline value minus the baseline value. Percentage change from baseline will be calculated as the change from baseline divided by the baseline value, multiplied by 100. If either the baseline or post-baseline value is missing, then change from baseline and percentage change from baseline will be set to missing.

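### Both UUI endpoints are analysed in men selected on any-cause leakage, with no requirement for urge leakage at baseline and no responder rule when baseline UUI is zero

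*SAP*

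**What the plan says.** **How leaks are counted.** For each leak the diary records "the main reason for the leakage (urge or other"), according to SAP 4.3.1. SAP 4.3.1.3 counts total incontinence over all leaks, "regardless of the choice of “Main Reason for Leakage". SAP 4.3.1.2 counts a UUI episode only where the subject "checked that they had “urge” as the main reason for the leakage".

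**Who is analysed.** SAP 3.1.6 defines incontinence at baseline by at least 8.0 micturitions and at least "1.0 urinary incontinence episodes per Diary Day", taken from the run-in diary. Protocol 9.3 uses the same two thresholds. Neither sets a minimum for UUI. For the UUI change from baseline, SAP 4.3.1.2 says: "The UUI endpoint will be analyzed for subjects with UI at baseline". SAP 6.2 assigns that analysis to FAS-I, and SAP 4.3.1.3 applies the same restriction to the UUI responder endpoint.

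**How the responder endpoint is derived.** SAP 4.3.1.3 says: "The achievement of at least a 75% reduction from baseline in average daily UII episodes is a binary variable" (UII is printed for UUI). SAP 4.3.4 says: "Percentage change from baseline will be calculated as the change from baseline divided by the baseline value, multiplied by 100". The only exception given there is for missing values.

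**Evaluability.** Protocol 9.3 requires that FAS-I subjects "have an evaluable baseline urgency urinary incontinence measurement" and an evaluable change in UUI. SAP 3.1.6 asks only for an evaluable change in urinary incontinence. SAP Section 9 does not list this difference.

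**The concern.** The selection variable (leaks of any cause) is wider than the outcome variable (urge leaks). Micturition, urgency and nocturia each have a baseline floor in the inclusion criteria, and total incontinence has one through FAS-I. UUI has none. A man with no recorded urge leaks at baseline is therefore in the denominator of two endpoints on which he cannot improve.

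Two things are at stake. The UUI change from baseline is second in the fixed sequence and stands ahead of IPSS Storage and volume voided, so its estimate should describe men who have the symptom. The responder endpoint is only exploratory, but its reported rates would be settled by a programming decision that the plan does not make.

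**Working it through.** The documents give no sample size, effect, SD or power for the UUI endpoints, so there is no UUI figure to reproduce. The check applies the SAP's definitions to a zero baseline and then shows the size of the effect under stated assumptions.

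**1. Can a zero-UUI man enter?** Take 2 other-cause leaks and 0 urge leaks per day. Any-cause leakage is 2.0, which meets the 1.0 threshold, and study entry already requires at least 8 micturitions. He is in FAS-I with baseline UUI = 0. The protocol's evaluability condition does not remove him, because zero is an evaluable value. Protocol 2.3 recognises stress and mixed incontinence, and no exclusion criterion names stress incontinence.

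**2. What do the formulas give?** Change = post − baseline. Percentage change = change / baseline × 100.

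| Baseline | Post | Change | % change | Rule: % change ≤ −75 | Rule: post ≤ 0.25 × baseline |
|---|---|---|---|---|---|
| 0 | 0 | 0 | 0/0, undefined | not computable | responder |
| 0 | 0.33 | +0.33 | undefined | not computable | non-responder |
| 1 | 0.25 | −0.75 | −75 | responder | responder |

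Two ordinary codings of the same 75% criterion agree when the baseline is above zero and disagree for 0 to 0. Treating the value as missing is a third option.

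**3. Dilution of the mean.** Let f be the share of FAS-I men with baseline UUI = 0. It is not in the documents, so 5% to 30% is assumed here for illustration. If these men contribute no treatment difference, the raw mean difference is multiplied by (1 − f): 0.95, 0.90, 0.80 and 0.70 at f = 5, 10, 20 and 30%.

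**4. Responder rates.** Assume true rates of 45% (placebo) and 55% (vibegron) in men with baseline UUI above zero, and assume that every zero-UUI man stays at zero. Coded as non-responders, each rate is p(1 − f). Coded as responders, it is p(1 − f) + f. The difference is 10(1 − f) points either way.

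| f | Coded non-responder | Coded responder | Dropped | Difference if kept |
|---|---|---|---|---|
| 10% | 40.5 vs 49.5 | 50.5 vs 59.5 | 45 vs 55 | 9 points |
| 20% | 36 vs 44 | 56 vs 64 | 45 vs 55 | 8 points |
| 30% | 31.5 vs 38.5 | 61.5 vs 68.5 | 45 vs 55 | 7 points |

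The coding alone moves each arm's rate by f, for example 20 points at f = 20%.

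**5. Power.** Suppose the full set would have 80% power if every man had urge leakage (two-sided 0.05, 1.960 + 0.842 = 2.802).
- Zero-UUI men kept, SD unchanged: Φ(2.802(1 − f) − 1.960) = 75.9, 71.3, 61.1 and 50.0% at f = 5, 10, 20 and 30%.
- Zero-UUI men kept, adding almost no variance: Φ(2.802√(1 − f) − 1.960) = 78.0, 75.7, 70.7 and 65.0%.
- Zero-UUI men excluded: the effect and SD are restored, but only n(1 − f) men remain. This gives the second formula again.

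Exclusion gains power in the first case and none in the second. The documents give no SD that would say which is nearer.

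**The case against.** The strongest reply is that this is declared design. Both documents name the endpoint throughout as UUI in subjects with urinary incontinence at baseline, with the same any-cause threshold, and incontinence (yes/no) is a stratification factor. That stands: the endpoint definition is a weakness, not a contradiction between protocol and SAP.

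The share of zero-UUI men may also be small. Every man needs at least 3 urgency episodes per day at run-in and baseline. Exclusion criteria 3 and 28 remove several other causes of leakage. This stands too, and it is why f is only illustrated. In addition, zero recorded UUI over about three days does not prove the absence of urge leakage. Treatment might limit later increases, so the (1 − f) factor is an assumption.

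On the responder endpoint, going from 0 to 0 is no reduction, so not attained is arguably the natural reading, and SAP 4.3.1.3 does not cite the percentage formula. That is reasonable, but the plan does not say it, and it still places men who cannot respond in the denominator.

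A reader might infer stronger things that the documents do not support:
- **False-positive risk or bias towards vibegron.** The restriction uses baseline data and applies equally to both arms, so it dilutes the effect and does not inflate type I error.
- **Demonstrated harm to the gate for IPSS Storage and volume voided.** Step 5 shows that this depends on a variance that is not given.
- **The evaluability mismatch as the cause.** UI and UUI come from the same diary records and zero is evaluable, so the protocol's wording would also admit these men.

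**Conclusion.** The point holds as a gap in definition. FAS-I admits men with no urge leakage at baseline, their UUI change cannot be negative, and no rule fixes their 75% responder status. The size is unknown because f is not given. Under the assumed 5% to 30% and no treatment difference in these men, the mean UUI difference falls by 5% to 30% of its value, and a 10-point responder difference becomes 9.5 to 7 points. Reported responder rates can differ by f between codings. The co-primary endpoints are not affected. The change-from-baseline endpoint matters more because of its place in the sequence, but a power gain from removing these men is not shown. The case for changing the plan rests on a clearer estimate and a defined responder status.

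**What to change.** Before unblinding:

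1. In SAP 4.3.1.3 and 6.3.1, restrict the 75% UUI responder analysis to FAS-I men with baseline UUI above zero.
2. For the UUI change from baseline (SAP 4.3.1.2 and 6.2), either apply the same condition or prespecify it as a sensitivity analysis. The second option leaves the population of the gated endpoint as the protocol states it.
3. Do not set a floor of 1.0 UUI episodes per day. A man with 0.67 urge and 0.67 other leaks per day is in FAS-I now and can improve, and such a floor would drop him.
4. Keep the any-cause criterion for the total-incontinence endpoint.
5. Reconcile the FAS-I evaluability wording (UUI in Protocol 9.3, UI in SAP 3.1.6) and declare the changes in SAP Section 9.

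The cost is one flag, a few sentences and a slightly smaller set for the UUI endpoints. No man with recorded urge leakage at baseline is lost. If the condition is made the main analysis of secondary endpoint 2, it changes the population of a gated endpoint and must be declared as such.
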